1.1 Synopsis

Protocol Title: A Prospective, Randomized, Crossover Study of the TheraPAP Compared to Automatic Adjusting Positive Airway Pressure (APAP) for the Treatment of Obstructive Sleep Apnea (OSA)

Protocol Name/Number: TheraPAP Adherence 1

Sponsor: SleepRes, PLLC

Rationale: TheraPAP is a prototype device (with full documented electrical and isolation safety) being developed by SleepRes for the treatment of obstructive sleep apnea (OSA) that can deliver either standard CPAP at a set pressure or what is called TPAP¹. TPAP is a pressure control algorithm that lowers the pressure from the set pressure at the beginning of inspiration and does not return the pressure to the full set level until about halfway through expiration. The present study, TheraPAP Adherence 1, is a randomized crossover study designed to examine the difference in therapy adherence between TPAP vs. CPAP alone in the treatment of OSA.

Overall Design:

The TheraPAP Adherence Study is a randomized, crossover study in treatment naive participants with OSA in which the adherence to therapy will be compared between TPAP and standard APAP. Because all participants will breathe on both therapy types and those therapy types are individually unique in feel, blinding is not possible. Participants will be chosen from a pool of patients who are PAP-naïve and who have received either a PSG (in-lab polysomnogram), split-night study (in-lab PSG and pressure titration) or home sleep study (HST) within the previous 3 months.

Upon signing an informed consent, participants will be randomly assigned to start on either the TPAP or APAP arms when they arrive at the office to pick up their Sefam S.Box with TheraPAP algorithms integrated. Each participant will then be given their new equipment and will be trained in proper use for both arms of the study so that they will not need to appear at the office again until the study is completed. In both the APAP and TPAP arms, participants will have their therapy set to 5-20 cmH₂O for three nights. The pressure range will then be narrowed to ± 2 cmH₂O around their 95% pressure level as assessed during the third night. This same pressure range will be used during the second arm for each patient.

¹ TPAP will be used herein to refer to the active treatment.

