Within the TPAP arm, participants will be set to a double Comfort Setting drop according to the following table. This drop schedule will be implemented even while the TPAP device is operating with automatic pressure adjustment.

P _{set} (cmH ₂ O)	Pressure Drop 1 (cmH ₂ O)	Pressure Drop 2 (cmH ₂ O)
5.0 - 5.9	0	0
6.0 - 6.9	1	0
7.0 - 7.9	2	0
8.0 - 8.9	2	1
9.0 - 9.9	2	2
10.0 - 20.0	2	3

Table 1: Comfort Setting Pressure Drops 1 and 2 to be used at the specified target set pressure to the patient.

Participants will use their starting therapy nightly at home for 6 weeks after which time they will undergo a washout period of 1 week where no therapy will be used. Following the washout period, they will initiate another 6-week usage with the second therapy. Afterward, they will return to the office to receive their permanent equipment. Phone calls as reminders to end the first arm, start the washout period, then to start the second arm will be made.

Immediately after both arms of the study are completed, the following will occur:

- Eligibility criteria will be reviewed and confirmed
- Participants will be asked to respond to the following
 - ESS (Epworth Sleepiness Scale)
 - FOSQ (Functional Outcomes of Sleep Questionnaire)

During the home use period, subjects will be called at the following time points during each arm of the study. At each time point, adverse events and compliance with the device will be assessed. Subjects using the device less than an average of 5 hours per night during the first week will be contacted on a more regular basis (weekly until 5 hour per night use is achieved) to address any problems and encourage use. If patients discontinue use of the device during the home use period, they will still be encouraged to return for all testing per protocol. If a patient refuses to come in for further testing, they will be considered a lost to follow up and excluded from efficacy analysis.

- 1 Day Phone Call (+2 days)
- 7 Day Phone Call (+/- 3 days)
- 14 Day Phone Call (+/- 3 days) IF deemed necessary per 7 Day compliance
- 28 Day Phone Call (+/- 3 days) Check-in

- Week 6 Phone Call (+/- 3 days) – End first arm, fill out questionnaires, start Washout Period
- Week 7 Phone Call (+/- 3 days) - Review protocol, start 2nd arm
- Week 12 (+/- 3 days) - Equipment Return

Data collected from the therapy device will include the following:

- Usage averaged over the 6-week period and nightly
- Leak averaged over the 6-week period and nightly

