4.2.2 First 6-Week Arm

Patients will start using their equipment the first night. The study coordinator will monitor usage nightly and after the third night with a minimum of 5 hours of use, they will remotely adjust the device pressure range to P95 ± 2 cmH₂O, using the P95 from the third night. This range will be used for the remainder of both arms of the study. During the study, daily remote collection of usage will be conducted both for later primary endpoint analysis and to guide further contact with the patient if they need help.

During usage in the first arm, P95 and AHI will be monitored to assure that the patient is receiving proper therapy. If P95 is near the upper limit and the AHI is above 5 events per hour, the range will be bumped up by 2 cmH₂O.

A contact schedule will also be set up with each patient to follow up on any needs for help. Similar interaction is customary with new CPAP patients. The schedule is as follows and will be conducted on both arms of the study:

- 1 Day Phone Call (+2 days)
- 7 Day Phone Call (+/- 3 days)
- 14 Day Phone Call (+/- 3 days) IF deemed necessary per 7 Day compliance
- 28 Day Phone Call (+/- 3 days)

Participants using the device less than an average of 5 hours per night during the first week will be contacted on a more regular basis (weekly until 5 hour per night use is achieved) to address any problems and encourage use. If patients discontinue use of the device during the home use period, they will still be encouraged to complete surveys per protocol. If a patient refuses to complete such surveys, they will be considered lost to follow up and excluded from efficacy analysis.

At the end of the 6-week period, patients will stop using any sleep therapy for 1 week as a washout between arms. The study coordinator will remotely switch the mode of operation of the

therapy device to that for the second arm employing the same pressure range as was used in the bulk of the first arm. Patients will be asked to fill out the questionnaires during this period (ESS and FOSQ). Additionally, the following data averaged over the 6-week period of the trial will be downloaded from the device:

- Usage
- Leak
- P95
- AHI

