4.2.3 Second 6-Week Arm

Following the one-week washout period, patients will start the second arm therapy for the next six weeks of nightly use. The procedure will be exactly the same as for the first arm, described above except that the device pressure range will be retained at the same settings that were present during the bulk of the first arm.

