5.9 Participant Discontinuation/Withdrawal from the Study

A participant may withdraw from the study at any time at his/her own request or may be withdrawn at any time at the discretion of the Investigator for safety, behavioral, or administrative reasons.

If the participant withdraws consent, the Sponsor may retain and continue to use any data collected before such a withdrawal of consent.

All participants who withdraw from the study with an ongoing AE must be followed until the event is resolved or deemed stable.

Participation may be terminated before completing the study and the reason recorded as follows:

- Withdrawal due to AE
- Participant withdrew consent at their own request, (e.g., intolerance to study procedures)
- At the discretion of the Investigator for safety, behavioral, or administrative reasons
- Other reasons, as they occur

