6.1 At Home Study

- **Methods:** Equipment taken home for the study (Sefam S.Box and associated patient interface materials) has been given European approval via a CE mark. Additions of TheraPAP algorithms, which have been tested extensively for safety and efficacy in our lab, will be evaluated on the S.Box machines via a testing procedure that is part of our quality system.
- Regular contact with patients according to the call schedule will be conducted and any problems will be discussed and reported.
- Study data reported by the S.Box (usage, P95, leak and AHI) will be averaged over a night and recorded daily through the S.Box remote access system, and will be stored according to HIPAA requirements at the sponsor's office.

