7.3 Populations for Analyses

For the purposes of analysis, the following analysis sets are defined:

Set	Description
Randomized	All participants who were randomized.
Modified Intent to Treat (mITT) Set	The mITT set comprises all participants who are randomized, undergo at least 1 night in either study arm, and have at least 1 measurement on the primary endpoint. Participants will be analyzed for equivalence.
Safety Set	The Safety Set consists of all participants who are randomized and undergo at least 1 night in either study arm.
Per Protocol (PP) Set	The PP Population consists of all participants without any major protocol violations and have considered to be evaluable for study analysis.

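### Participants who stop the device and then refuse surveys or testing are dropped from efficacy analysis, although their usage, the primary endpoint, is still recorded remotely and the mITT set keeps them

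*Protocol*

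**What the plan says.** Section 3 makes nightly usage, TPAP versus APAP, the primary endpoint. ESS and FOSQ are secondary.

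Usage needs neither a survey nor a visit. Section 4.2.2 states that "daily remote collection of usage will be conducted both for later primary endpoint analysis", and section 6.1 says the device data "will be averaged over a night and recorded daily through the S.Box remote access system".

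Two passages deal with participants who discontinue the device during home use:

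- Section 4.2.2 encourages them to complete the surveys, then adds: "If a patient refuses to complete such surveys, they will be considered lost to follow up and excluded from efficacy analysis". Section 4.2.3 carries this into the second period: "The procedure will be exactly the same as for the first arm", apart from the pressure range.
- Section 1.1 (Synopsis) encourages them to return for testing, then adds: "If a patient refuses to come in for further testing, they will be considered a lost to follow up and excluded from efficacy analysis".

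Section 7.3 defines the analysis sets: "The mITT set comprises all participants who are randomized, undergo at least 1 night in either study arm, and have at least 1 measurement"; the measurement meant is one of usage. It sets no survey or visit condition and attaches a comparative (equivalence) analysis to this set. It does not say which set carries the primary analysis.

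**The concern.** In an unblinded adherence trial, giving up on one of the two therapies is part of the outcome. The rule takes effect only after a participant has stopped, and then depends on a second post-randomization act, refusing a questionnaire or a visit. Low users stay in, as do stoppers who fill in the forms. Stoppers who refuse go out, with all the usage already recorded for them. If stopping or refusing is more frequent on one therapy, the TPAP-APAP difference is biased, and nothing in the protocol tells us in which direction.

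The text is also inconsistent in two ways. A stopper with recorded nights belongs to the mITT set but is outside efficacy analysis, and no section says which statement prevails. If the question is left open, it could be settled after usage has been seen. Secondly, the two triggers differ, and the Synopsis trigger has little to refer to: the same Synopsis says of participants that "they will not need to appear at the office again until the study is completed", and the Schedule of Activities places ESS and FOSQ at home, leaving only equipment return and handover for the final office visit.

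**Working it through.** **The passages side by side**

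| Participant | Usage recorded? | mITT (7.3) | Efficacy analysis (1.1, 4.2.2) |
|---|---|---|---|
| Low user, never stops | yes | in | in |
| Stops, completes surveys and visit | yes | in | in |
| Stops, refuses surveys or testing | yes | in | out |

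Only the last row conflicts. What separates it from the row above is cooperation with secondary assessments, not availability of the primary endpoint.

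**The plan's own figure**

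Section 7.1 states about 82% power for 28 evaluable participants, a difference of 0.5 h, an SD of paired differences of 1 h and one-sided 5%. The noncentral t calculation with 26 degrees of freedom gives 82.4%, so the figure reproduces. The issue here is bias, not this calculation.

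**Size of the bias**

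Inputs from section 7.1: a true difference of 0.5 h, and about 20% dropout as a guide to how much stopping is plausible (not all dropout would arise from this rule).

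Assumptions, not in the protocol:

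- usage of 6 h per night;
- stopping after night 14 of 42, so the loss on that arm's mean is L = 6 × (1 − 14/42) = 4 h;
- pA and pT, the proportions stopping on APAP and TPAP, with nobody stopping on both;
- r, the share of stoppers who refuse;
- both periods started.

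The non-stoppers' difference is d = 0.5 − (pA − pT) × L. After exclusion a fraction 1 − r(pA + pT) remains, and the analysed difference is

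d + (1 − r)(pA − pT)L / [1 − r(pA + pT)].

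For pA = 0.15, pT = 0.05: d = 0.5 − 0.10 × 4 = 0.10. With r = 0.5 the result is 0.10 + 0.20/0.90 = 0.322.

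| Stopping APAP / TPAP | d (h) | r = 1 | r = 0.5 | r = 0.25 |
|---|---|---|---|---|
| 15% / 5% | 0.10 | 0.100 (bias −0.40) | 0.322 (−0.18) | 0.416 (−0.08) |
| 5% / 15% | 0.90 | 0.900 (+0.40) | 0.678 (+0.18) | 0.584 (+0.08) |
| 7.5% / 2.5% | 0.30 | 0.300 (−0.20) | 0.405 (−0.095) | 0.454 (−0.05) |
| 10% / 10% | 0.50 | 0.500 (0) | 0.500 (0) | 0.500 (0) |

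A simulation of 2,000,000 participants (between-subject SD 1 h, SD of paired differences 1 h, all stoppers refusing) agrees. At 15%/5%, complete data give 0.49 h and the exclusion rule 0.10 h. At 10%/10% they give 0.47 and 0.50 h.

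**A different mechanism, under the null**

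This uses 36 participants, paired differences N(0,1) and 40,000 runs. The 20% with the largest deficit on each therapy count as its stoppers, and some are excluded.

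| Share excluded, TPAP-side / APAP-side stoppers | Mean shift (h) | One-sided type I error |
|---|---|---|
| 50% / 50% | about 0 | 5% |
| 50% / 25% | +0.08 | 13% |
| 50% / 0% | +0.16 | 24% |
| 0% / 50% | −0.16 | 0.5% |

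**Check of the remedy**

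Take 15%/5% stopping and suppose every first-period stopper never starts period 2. Complete data give 0.49 h and the exclusion rule 0.10 h. Zero for post-stop nights, with the unstarted period treated as missing in a mixed model, gives 0.41 h. Scoring the whole unstarted period as zero gives 0.19 h.

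**The case against.** The best defence is that section 7.3 names no set for the primary analysis and also defines a per-protocol set. The exclusion could be meant for that set only, with mITT keeping everyone, and an unseen SAP may say so. That is possible, but neither passage limits the exclusion in this way. Both say efficacy analysis without qualification, and a SAP that used mITT for usage would have to depart from them.

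The large figures depend on their assumptions. At 15%/5% stopping with a 4 h loss, 0.40 h of the 0.50 h effect comes from stoppers by construction, so removing them all must leave 0.10 h. That case needs a 3:1 imbalance, universal refusal and stopping that uses up the whole 20% dropout allowance. Milder cases give 0.05 to 0.095 h. This stands: the numbers show what the rule can do, not what it will do.

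Keeping stoppers also has a price in precision. With the same inputs the variance of the paired difference becomes 1 + 16 × (0.20 − 0.01) = 4.04, an SD of about 2.0 h, and power with 36 participants for 0.5 h falls to about 43%. At 7.5%/2.5% the SD is 1.6 h and power about 58%. This is a reason to review the SD in section 7.1, not to exclude on the outcome.

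Finally, one could contrast the rule with section 5.9, under which "the Sponsor may retain and continue to use any data collected before such a withdrawal of consent", so that declining a survey seems to cost more primary data than withdrawing consent. But that clause permits retention and does not define an analysis set, so little should rest on it.

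**Conclusion.** The concern holds. As written, sections 1.1 and 4.2.2 discard observed primary-endpoint data because of post-randomization behaviour tied to the outcome, and they cannot be reconciled with an mITT analysis of usage. This is an explicit rule in the protocol, not detail left to a SAP, and it should be corrected before any usage data are analysed.

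The size cannot be fixed from the protocol. Under the stated assumptions the bias runs from about 0, when stopping is balanced, to 0.40 h, or 80% of the 0.5 h design difference. Its sign is unknown. The upper end needs strongly unequal stopping and refusal by every stopper. The conflict between the passages depends on none of these assumptions.

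**What to change.** 1. In sections 1.1 and 4.2.2, delete the clause that excludes these participants from efficacy analysis, and use one wording for the trigger in both places.
2. State that usage is analysed in the mITT set from all remotely recorded data, and that refusing surveys or the return visit makes only ESS and FOSQ missing.
3. Within a period the participant has started, count nights after stopping as 0 h unless consent is withdrawn.
4. Do not score a second period that was never started as 0 h. Treat it as missing in the crossover model, for example a mixed model using the available period, with a sensitivity analysis.

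Items 1 and 2 remove the contradiction on their own. Items 3 and 4 could sit in the SAP if it is written before the data are seen.

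The cost is a deletion in two passages and a short added rule, with no new data collection. Near-zero usage may raise the variance and make the estimate less favourable, so the SD assumption in section 7.1 should be reviewed alongside. Treating an unstarted period as missing rests on a missing-at-random assumption; in the check above it recovered 0.41 h of 0.49 h, not all of it.

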2.2.3 Biological Rationale

TPAP is an innovative device/algorithm designed to deliver a lower inspiratory than expiratory PAP. The drop in inspiratory pressure can be modulated during the inspiratory phase. Previous research has shown that reducing inspiratory PAP by placing a resistor in the inspiratory line can enhance subjective comfort and decrease leaks when compared to CPAP, despite maintaining a similar residual apnea-hypopnea index (AHI). However, the resistor could only provide a fixed inspiratory PAP reduction based on existing PAP settings. TPAP addresses this limitation by allowing for adjustable drops in inspiratory PAP throughout the inspiration phase, offering a potentially more personalized and adaptive therapeutic approach.

3 Endpoints

	Endpoints
Primary	
• Nightly adherence (usage) with device (TPAP versus APAP)
Secondary	
• Evaluation of P95, Leak and AHI over each 6-week period• 6-week Subjective Questionnaires (TheraPAP versus APAP) following each arm
◦ ESS◦ FOSQ• Adverse Event rate
Safety Endpoints²	
• Spontaneous adverse events

² Although there will not be any direct treatment vs. control comparison here, we will assume that CPAP is safe and that any abnormal value recorded in the next morning compared to the evening before the polysomnography is due to treatment with TPAP.

4 Study Design

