4.3 End of Study Definition

Once the second 6-week arm is over and questionnaires have been completed, the patients will return their equipment to the office. Once the equipment is returned, the participants' involvement in the study will be complete and they will be able to receive their study incentive. They will also then be given their regular take-home equipment with usage instructions.

5 Study Population

Eligible participants will be recruited from the pool of PAP-naïve patients who have undergone some form of sleep study and will be receiving CPAP therapy equipment.

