7.1 Sample Size Determination

Sample sizes are estimated to achieve 80% power based on a 1-sided 5% significance level. As this is an exploratory proof of concept trial, a 1-sided 5% significance level was selected. The within subject standard deviation is assumed to be 1 hour and the minimum treatment difference is assumed to be 0.5 hours.

When there are 2 treatments and a sample size of 14 in each of the 2 sequences, a 2x2 Williams Crossover Design will have approximately 82% power to detect a minimum pairwise difference of 0.5 or greater, assuming that the standard deviation of the paired differences is 1 at a one-sided 5% significance level.

Assuming ~20% dropout and total of 36 patients (18/sequence) is planned.

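### First-arm ESS and FOSQ may be completed off therapy during the washout week, unlike the synopsis rule and the second arm, so the two periods may be measured in different treatment states

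*Protocol*

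**What the plan says.** The protocol places the ESS and FOSQ in several sections.

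- **Section 4.2.2, end of the first arm.** "At the end of the 6-week period, patients will stop using any sleep therapy for 1 week as a washout between arms". After a sentence on switching the device remotely to the second mode, it continues: "Patients will be asked to fill out the questionnaires during this period (ESS and FOSQ". No day is named. The call list in this section ends at Day 28, so it contains no Week 6 contact.
- **Section 1.1, call schedule.** The Week 6 call (window of 3 days either side) reads: "End first arm, fill out questionnaires, start Washout Period".
- **Section 1.1, assessments.** The list containing the ESS and FOSQ is introduced by: "Immediately after both arms of the study are completed, the following will occur".
- **Section 1.2, Schedule of Activities.** Both forms appear under a post-6-week heading for each arm, as home activities, without a day.
- **Section 4.2.3, second arm.** "The procedure will be exactly the same as for the first arm, described above except that the device pressure range will be retained" at its first-arm settings.
- **Section 4.3.** "Once the second 6-week arm is over and questionnaires have been completed, the patients will return their equipment to the office". No washout after the second arm is described.
- **Section 3, Endpoints.** The forms are a secondary endpoint: "6-week Subjective Questionnaires (TheraPAP versus APAP) following each arm".

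**The concern.** In a two-period crossover, each period's score should describe the participant in the same state relative to treatment. As Section 4.2.2 is written, a first-arm form may be completed after anything from no untreated nights to a full untreated week. The second arm has no planned untreated week. A coordinator following Section 4.2.2 and one following the synopsis could collect first-arm scores in different states, and both would be compliant.

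The washout is there so that the first therapy's effect can fade before the second begins. Collecting the first therapy's scores in that same week works against that purpose. If part of the difference between devices fades with the overall benefit, the period-1 contrast shrinks, and no analysis can recover what was not present when the form was completed. A completion day that varies between participants would also add noise.

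**Working it through.** **1. Which period Section 4.2.2 means.** The sentence before the device switch stops all therapy for one week, and Section 4.1 places that switch within the washout. The next sentence of Section 4.2.2 refers separately to the 6-week period when it lists the device data. The questionnaire sentence therefore points to the washout.

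**2. Length of the possible gap.** Nominally it is 0 to 7 nights. If the 3-day windows on the Week 6 and Week 7 calls were used in opposite directions, the limit would be (49 + 3) - (42 - 3) = 13 days. That is an outer limit, not the planned timing.

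**3. Second arm.** Section 4.3 gives an order (arm over, forms done, equipment returned) but no interval. The calendar does not supply one: 6 + 1 + 6 = 13 weeks, whereas the synopsis puts equipment return at Week 12. Section 4.2.3 carries over the first-arm procedure, but there is no untreated week in which to repeat it. A gap near zero is the natural inference, though it is not stated.

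**4. The plan's own power figure.** None is given for the ESS or FOSQ. For usage, Section 7.1 states: "Sample sizes are estimated to achieve 80% power based on a 1-sided 5% significance level". With a difference of 0.5, SD of paired differences 1, and 14 per sequence (n = 28, df = 26), the noncentrality is 0.5 × √28 / 1 = 2.65. The noncentral t gives 82.4%, which reproduces the stated figure of about 82%.

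**5. Effect on the questionnaire contrast.** Let d be the true TPAP-APAP difference, f the fraction lost before the first-arm form is completed, and s an off-therapy shift common to both devices. Take the within-participant differences, TPAP minus APAP:

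- TPAP first: (1 - f)d + s
- APAP first: d - s
- Mean of the two sequence means: [(1 - f)d + s + d - s] / 2 = (1 - f/2)d

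The shift s cancels and the loss f does not. This takes the second-arm loss as zero. With a second-arm loss g, the share kept is 1 - (f + g)/2.

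| f (assumed) | Share kept, 1 - f/2 | Illustrative power |
|---|---|---|
| 0 | 100% | 82.4% |
| 0.10 | 95% | 78.9% |
| 0.25 | 87.5% | 72.9% |
| 0.50 | 75% | 61.3% |
| 1 | 50% | 36.1% |

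The power column borrows the primary endpoint's standardized difference of 0.5 with n = 28. The protocol makes no such assumption for the questionnaires, so the column shows only how sensitive power is to f.

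**6. When the common shift would matter.** It cancels with equal sequences or with period adjustment. In an unadjusted paired mean with an 18:10 split and a shift of 1 SD, the expected estimate is 0.5 + (18 - 10)/28 = 0.79 instead of 0.50. Simple even/odd allocation of 28 gives a split of 18:10 or worse with probability 0.18. The analysis model may be set in an analysis plan that is not shown, so this is a caution only.

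**The case against.** The strongest defence is that the passages can be read together. All of them place the forms after the arm ends. The Week 6 call closes the arm, prompts the forms and opens the washout in one contact, so a form completed then or on the first washout day nearly satisfies every section. On that reading the defect is an unfixed day and a difference in order, and seven untreated nights is the worst case allowed. This stands as a limit on size. It does not remove the defect, because Section 4.2.2 permits any day of the week and its own call list omits the Week 6 call.

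Three stronger readings are tempting and are not supported:

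- **That the contrast is diluted as a matter of fact.** This needs the difference between devices, not only the overall level, to fade within days. The protocol gives neither a recall frame for the forms nor a rate of decay. Having a washout shows that carryover was a concern, not how fast a questionnaire difference disappears.
- **That second-arm forms follow therapy directly.** This is inferred from the synopsis and Section 4.3; no window is stated.
- **That correcting one sentence is enough.** The synopsis lists no questionnaire contact at the end of the second arm, only equipment return, so a time point has to be added.

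It is also fair to say that these are secondary endpoints in a trial described as exploratory, and that attenuation would push toward no difference and would not create an apparent TPAP advantage.

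**Conclusion.** The point holds as an inconsistency in assessment timing with a possible cost. The protocol has two rules for the first-arm ESS and FOSQ, one of which allows completion off therapy, and no common window for the two arms. This does not depend on f.

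The size of any attenuation is unknown. It is near zero if forms are completed at the call or on the first washout day, and reaches half of the contrast only if the whole difference is lost in the first arm and none in the second. The (1 - f/2) rule rests on f, which is assumed, and on second-arm forms being completed without loss, which is inferred. A common off-therapy shift is a period effect and does not attenuate the contrast. Device-recorded usage, the primary endpoint, is unaffected, as are the stated power and sample size. The point is worth correcting because the loss, if it occurs, happens at data collection and cannot be repaired in the analysis.

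**What to change.** 1. Reconcile Section 4.2.2 with the synopsis: first-arm ESS and FOSQ are completed at the Week 6 call, before therapy is stopped. Add that call to the Section 4.2.2 contact list.
2. Add a matching questionnaire time point at the end of the second arm, ahead of equipment return, in Sections 1.1, 1.2, 4.2.3 and 4.3. While doing so, reconcile the Week 12 return with a schedule that runs to Week 13.
3. Define one window for both arms relative to the last treated night, not the call date, since the call itself can move by 3 days. Making the arms symmetric is not enough: equal delays in both would keep 1 - f, which is less than 1 - f/2.
4. Record on each form the completion date and the number of nights since last use, so that departures can be seen and examined.

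The cost is small scheduling changes, one added contact or task at the end of the second arm, and two extra recorded items per form. The sample size and the primary analysis do not change.
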